#### **Grade 4:**

- Any bleeding associated with severe hemodynamic instability (hypotension;  $>50$ mm/Hg fall or  $>50\%$  decrease in either systolic or diastolic blood pressure, with associated tachycardia (heart rate increase of  $> 20\%$  for 20 minutes) and requiring RBC transfusion over routine transfusion needs
- Fatal bleeding from any source
- Retinal bleeding with visual impairment (Visual impairment is defined as a field deficit, and patients with suspected visual impairment require an ophthalmologic consult for documentation)
- CNS symptoms with non-traumatic bloody lumbar puncture
- CNS bleeding on imaging study with or without dysfunction

## Appendix B- Flow Diagram of Study Events

(Each cohort = 8 patients)

## Appendix C- Definition of Myocardial Infarction

Definition of Myocardial Infarction (two or more of the following):

1. hs Troponin I or hs Troponin T level greater than the local lab reference range for normal.
2. Electrocardiograms (EKGs; at least two) showing changes from baseline or serially in ST-T and/or Q-waves that were 0.03 seconds in width and/or greater than one-third of the total QRS complex in two or more contiguous leads.

**NOTE:** Other EKG findings consistent with a diagnosis of myocardial infarction may also be considered a myocardial infarction.

[figure not shown]
3. Clinical indications consistent with myocardial infarction as seen by prolonged (> 20 min) chest pain not relieved by rest and/or nitrates
4. Radiologic evidence as seen by
  - A. Angiographically documented coronary artery occlusion, or
  - B. Imaging evidence of loss of viable myocardium

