Routine Chemistry: Na, K, Cl, CO2, Glucose, BUN, Creatinine, Albumin, Total Bili, Ca, AST, Alkaline Phosphatase, ALT, GGT, LDH, Total Cholesterol, Total Protein			X		X	X					
Special Chemistry hsTroponin I or T Assay			X		X	X					
Draw archive sample	X									X	

Evaluation	Initial Screen	Rescreen (if applicable  )	Day 1  Base Line -2 hr pre-infusion	1 hr post infusion ± 15min	6 hr post -1 or +2 hr	Day 2 24 hr post ± 3 hr	If hospitalized			Day 6 (+ 4 days)	Day 30 (+2 days) (by phone)								
							Day 3	Day 4	Day 5										
 Rescreening performed on those patients who passed eligibility criteria, were not actively bleeding at time of initial screen, and started bleeding within 4 weeks. Patients who were initially screened within 4 days (+6 hrs) do not need to be re-screened except for WHO bleeding assessment and CBC.																			
 Baseline may occur on the same day (within 24 hours) as either Initial Screen or Rescreen. The WHO assessment, CBC and coagulation must be collected at baseline, not more than 2 hours prior to infusion. Red cell transfusion must be specifically related to treatment of bleeding within 24 hours of onset of bleeding.																			
 Chart review for SAEs (only) needs to include data from day 1 though Day 30 (+2 days). Phone call with patient is to confirm if the patient had an SAE or required emergency medical care at an outside facility.																			
 Complete physical exam to include height, weight, general assessment of health by history and medical exam including neurological exam. History to include previous transfusion with red blood cells, plasma and/or platelets.																			
 Abbreviated Physical Exam to include general appearance, cardiovascular, respiratory, extremities, abdomen and head and neck.																			
 In the event of the transfusion of a blood component after infusion of Thrombosomes on Days 1-6, CBC results are required from a sample collected within 8 hours or less prior to the transfusion and within 1-hour (+30 min) post transfusion.																			
 Daily CBC required, but ALL CBC data for each patient during the hospitalization phase through Day 6 must be collected and entered into the database.																			
 If TEG or ROTEM testing is available, include samples for the record.																			

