## 1.18 Risk Assessment

### 1.18.1 *Foreseeable or Potential Risks*

The following risks to participation of this clinical trial are outlined in the Table 5 below:

Table 5. Potential Study Risks	
Trial Stage	Risks Identified
AEs Possibly Related or Related to Thrombosomes Infusion during Phase 1 Study No. 2011-1	

• Prothrombin Level Increased (Elevated Prothrombin Fragment 1+2)

• White Blood Cell Count Increased

• Fibrin D-dimer Increased

• Electrocardiogram T-wave Abnormal

• Autoantibody Positive (Platelet Autoantibody)

AEs Associated with Blood Product Infusion including Platelet Infusion which may also be associated with Thrombosomes	

• Hematoma or localized infection at the venipuncture site

• Nausea/vomiting, dizziness/ fainting, seizures

• Allergic reaction (flushing, itching, hives, abdominal cramps, difficulty breathing, chest pain, or bronchospasm, which may vary in severity from mild to life-threatening)

• Difficulty breathing, chest pain, or bronchospasm, which may vary in severity from mild to life-threatening)

• A minimal risk of cancer cannot be completely and definitely ruled out

• Immune suppression

• Infectious disease transmission

• Cardiac failure

• Noncardiac pulmonary edema

• Stroke

• Thrombocytopenia

• Formation of platelet antibodies

• Thrombosis – arterial or venous

• Pulmonary Embolism

• Heart attack

• Death

Miscellaneous	

• Breach of patient confidentiality

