## **Appendix D- Definition of ALI Adapted from NHSN Biovigilance Component Hemovigilance Module Surveillance Protocol v2.4**

[figure not shown]
ALI is defined as the presence of the following:

- NO evidence of acute lung injury (ALI) prior to infusion, and
- Radiographic evidence of bilateral infiltrates, and
- No left atrial hypertension (i.e., circulatory overload) as determined by clinical signs or left atrial pressure measurements, and
- Hypoxemia defined by any one of these methods:
  - PaO2/FiO2 less than or equal to 300 mm Hg
  - Oxygen saturation less than 90% on room air
  - Other clinical evidence

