- Definite: An association exists between receipt of the investigational product and occurrence of the event; any association with other factors has been ruled out.

***Suspension Rule:*** This study will be suspended if an SAE is reported by a Principal Investigator (PI) who believes that the event is possibly, probably, or definitely related to the use of Thrombosomes but does not meet the study's stopping criteria (described below). Following SAE reporting by the PI, the Sponsor will corroborate relatedness of the SAE to the study product and suspend the enrollment and infusion of patients until further evaluation of the SAE is completed. A DMC, along with the Medical Monitor and PI who treated the patient, will meet ad hoc to review characteristics and outcomes of the event. The DMC will formulate final conclusions regarding SAE causality and provide recommendations for whether the study should proceed without changes, proceed with changes, or not proceed at all.

***Stopping Rule:*** The Sponsor will stop patient enrollment if a reported SAE satisfies all 3 of the following criteria: (1) reported as death, a thrombotic or embolic event, an acute lung injury, or anaphylaxis; (2) reported within 48 hours of infusion with Thrombosomes (except for anaphylaxis, requiring reporting within 4 hours of infusion); and (3) considered to be probably or definitely directly related to Thrombosomes. If the study is stopped, the study will resume only after a complete review of the data has been performed by the Medical Monitor, all PIs, and the DMC and a determination has been made of reasonable doubt that the event is related to the product. Note that thrombotic and embolic events, collectively, include myocardial infarction, pulmonary embolism, venous thromboembolism, stroke, and transient ischemic attack. The CSP Appendices C, D, E, and G provide definitions for these events, as well as acute lung injury and anaphylaxis.

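### Appendix C's troponin criterion for myocardial infarction ignores the pre-infusion value, so a patient with an unchanged raised troponin needs one further sign instead of two

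*Protocol*

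**What the plan says.** Appendix C opens with "Definition of Myocardial Infarction (two or more of the following", followed by four items: troponin, EKG, chest pain and imaging.

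- **Item 1 (troponin):** "hs Troponin I or hs Troponin T level greater than the local lab reference range for normal". There is no baseline, rise or timing condition.
- **Item 2 (EKG):** at least two EKGs "showing changes from baseline or serially in ST-T and/or Q-waves", with width or QRS and contiguous-lead terms. A note adds: "Other EKG findings consistent with a diagnosis of myocardial infarction may also be considered a myocardial infarction".
- **Appendix D (acute lung injury)** requires "NO evidence of acute lung injury (ALI) prior to infusion".

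Protocol Table 4 schedules the "Special Chemistry hsTroponin I or T Assay" at Day 1 baseline, 6 h and 24 h, but not at screening or rescreening. Protocol 1.9.8 places MI, as defined in Appendix C, among thrombotic or embolic events. Protocol 1.9.9 makes thromboembolic events part of the primary endpoint. SAP 3.2 adds no definition of its own: "The CSP Appendices C, D, E, and G provide definitions for these events". SAP 8.1, which plans the event summaries, refers to SAP 3.2 for definitions.

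**The concern.** The pre-infusion troponin is collected but plays no part in deciding whether an event is an MI. Patients with a raised troponin can be enrolled: the cardiac exclusion in Protocol 1.11.2 is by history only, and troponin is not a screening test. For such a patient item 1 is met before the product is given, and it stays met if nothing changes.

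At stake is the count of thromboembolic events, the safety outcome of most interest for this product. With 8 patients per cohort, a single event that owes half its classification to a pre-existing abnormality could alter how a dose level looks.

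**Working it through.** The plan states no figure for this definition, so there is nothing to reproduce. The check compares the text, counts the combinations and adds an illustration.

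**1. Use of the pre-infusion state**

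| Definition | Refers to the pre-infusion state? |
|---|---|
| Appendix C item 1, troponin | No |
| Appendix C item 2, EKG | Yes: change from baseline, or serial change |
| Appendix D, lung injury | Yes: absent before infusion |

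Nothing elsewhere supplies the missing term. SAP 8.3 plans change-from-baseline and shift tables for chemistry, including troponin, but does not link them to event classification.

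**2. Effect on the two-of-four rule**

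Items 2 to 4 can be present or absent in 2 × 2 × 2 = 8 combinations.

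- Troponin in range: at least two of items 2-4 are needed, so 4 of 8 combinations qualify.
- Troponin raised before infusion and unchanged: at least one is needed, so 7 of 8 qualify.

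These are counts of combinations, not probabilities.

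**3. Size of one event**

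1/8 = 12.5 percentage points of a cohort's rate.

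**4. Illustration under assumed rates**

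Let r be the proportion with a raised, stable baseline troponin, and q the chance that each of items 2-4, as fully worded, arises from another cause. Assume independence and no new troponin rises.

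- At least one of items 2-4: a = 1 − (1 − q)³
- At least two: b = 3q²(1 − q) + q³
- Per patient as written: r·a + (1 − r)·b. If a stable elevation does not count: b
- At least one event in 24 patients: 1 − (1 − per-patient probability)²⁴

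For q = 2%: a = 1 − 0.98³ = 0.0588, and b = 3 × 0.0004 × 0.98 + 0.000008 = 0.00118.

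- r = 5%: 0.05 × 0.0588 + 0.95 × 0.00118 = 0.00407, giving 9%.
- r = 30%: 0.30 × 0.0588 + 0.70 × 0.00118 = 0.01847, giving 36%.
- Stable elevation not counted: 0.00118, giving 2.8%.

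| Assumed q | As written, r = 5% to 30% | Stable elevation not counted |
|---|---|---|
| 1% | 4% to 20% | 0.7% |
| 2% | 9% to 36% | 2.8% |
| 5% | 29% to 69% | 16% |

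At r = 5% to 30%, the expected number of patients with a raised baseline is 24 × 0.05 = 1.2 to 24 × 0.30 = 7.2. The documents support none of these values of r or q. The spread shows that the frequency cannot be stated. Only the direction can.

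**5. Would a bare above-baseline test be enough?**

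Suppose a stable troponin varies only by measurement noise. The baseline, 6 h and 24 h values are then exchangeable and, without ties, each is equally likely to be the highest. Baseline is highest with probability 1/3, so at least one later value exceeds it with probability 1 − 1/3 = 2/3. About two in three stable elevations would pass such a test.

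**The case against.** **Investigator judgment comes in between.** Protocol 1.9.8 introduces these definitions for stopping-rule events, and 1.9.9 does not cite Appendix C. The diagnosis is the investigator's, and Protocol 1.22.6.1 does not treat mild, clinically non-significant laboratory changes as adverse events. No program is specified to score Appendix C from the data. This stands in part: the count is not automatic. But SAP 8.1 points to SAP 3.2 for definitions, and SAP 3.2 adopts Appendix C, so an investigator who follows the definition meets the gap.

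**The second sign is not easily met.** This stands. Item 2 asks for at least two EKGs and has contiguous-lead terms, and only one post-infusion EKG (6 h) is scheduled. If baseline and 6 h count as the pair, scheduled tests can satisfy it. If two EKGs must each show change, an unscheduled one is needed. Item 3 needs pain consistent with MI that is not relieved by rest and/or nitrates. A reader might infer from "Electrocardiogram T-wave Abnormal" in Protocol Table 5 that the second sign will be common. That entry gives no rate. The earlier human study described in Protocol 1.6 and 1.9.1 was in healthy volunteers, and a T-wave abnormality alone does not establish item 2.

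**The trial could stop on a spurious MI.** A reader might infer this, but the documents do not support it as an automatic result. Protocol 1.9.8 also requires a serious event within 48 h that is probably or definitely related. Under 1.22.6.2, probably related means that the patient's clinical state cannot explain the event, and a stable pre-infusion elevation argues against that. The suspension rule can act on a possibly related serious event, but the sponsor must first confirm relatedness.

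**A sensitive definition suits a Phase 1 study, and the data will be listed anyway.** Sensitivity is defensible for a product with some properties of partially activated platelets (Protocol 1.15.1). Raised troponin plus a qualifying new sign may also be a true event. This is a reason to flag such events and keep them in view, not to remove them. Troponin values (Listing 16.2.6.3) and the events (Listing 16.2.5.8) are planned as separate listings, and nothing carries the baseline value into the count.

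**Conclusion.** The gap is real and modest. Item 1 of Appendix C can be met by a troponin that was raised before infusion and never changed, which lowers the requirement from two further signs to one. Neither the eligibility criteria nor the SAP closes it. One event classified this way is 12.5 points of a cohort's rate.

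The textual finding and the combination count need no assumption. Any statement of frequency does, because the documents give no rate of raised baseline troponin or of the other signs; the percentages above are illustrations. The conclusion concerns how thromboembolic events are classified and reported. It does not extend to saying that the study would stop, or that every event classified this way is false.

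**What to change.** In the SAP (8.1 and Listing 16.2.5.8):

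1. For each MI, show the Day 1 pre-infusion troponin beside the post-infusion values on the same assay. The assay matters because Table 4 allows troponin I or T.
2. Flag events that meet Appendix C only because of a troponin already above range before infusion, that is, with no more than one of items 2-4 present.
3. Report thromboembolic counts per cohort with and without the flagged events, and name the table that carries them. No table title in SAP Appendix 2 refers to these events.
4. If a post-infusion rise is to lift the flag, set its size in advance and make it exceed assay variation. A bare above-baseline test would be passed by noise about two times in three.

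The sponsor's clinicians should separately reconcile Appendix C item 1 with item 2 and Appendix D, so that the endpoint and the stopping rule use one definition.

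Cost: the SAP changes need a few sentences, one flag and one extra row per count, with no new data collection. A change to Appendix C itself is a protocol modification under section 1.22.4, with IRB approval and submission to FDA.

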## **Appendix D- Definition of ALI Adapted from NHSN Biovigilance Component Hemovigilance Module Surveillance Protocol v2.4**

[figure not shown]
ALI is defined as the presence of the following:

- NO evidence of acute lung injury (ALI) prior to infusion, and
- Radiographic evidence of bilateral infiltrates, and
- No left atrial hypertension (i.e., circulatory overload) as determined by clinical signs or left atrial pressure measurements, and
- Hypoxemia defined by any one of these methods:
  - PaO2/FiO2 less than or equal to 300 mm Hg
  - Oxygen saturation less than 90% on room air
  - Other clinical evidence

## Appendix E- DVT and PE Algorithm Pages from ICSI Guideline

## Pulmonary Embolism (PE) Diagnosis Algorithm

Text in blue in this algorithm  
indicates a linked corresponding  
annotation.

## **Appendix F – Instructions for Reconstitution and Preparation of Thrombosomes for Administration**

Study sites receiving, storing, preparing and administering Thrombosomes should be operating under BSL-2 workplace biosafety measures as applied in the blood establishment setting (AABB Technical Manual 19th edition chapter 2, Facilities, Work Environment and Safety). These biosafety measures address agents of moderate potential hazard to personnel and the environment, usually from contact-associated exposure to certain infectious agents. Blood banks and laboratories typically operate under these measures, and pharmacies may also designate personnel, equipment, areas and procedures for the handling of such blood products.

### ***Appendix F.1        Supplies and Equipment Required***

Investigational product is Thrombosomes. Thrombosomes are prepared from pooled human blood product and supplied for this trial as a lyophilized cake in a stoppered vial(s) for reconstitution with 10 ml sterile Water for Injection (WFI).

#### **Supplies and Equipment for Reconstitution of Thrombosomes and Preparation of Doses**

- Sterile Water for Injection, USP (may be used for multiple reconstitutions but discard at the end of the shift or day)
- Sterile 10 and 20 ml syringes
- Sterile Closed System Transfer Device (CSTD) (e.g. Chemotherapy Dispensing Pin, Universal Vial Spike with Clave or equivalent)
- Alcohol wipes
- Labels for syringe for final dose
- Sterile syringe tip cap (dual function)
- Hemo-Nate® Filter, 18 micron blood filter, (Product #402009, Utah Medical Products, Midvale, UT)

#### **Supplies and Equipment for Administration of Dose**

- IV administration set
- Syringe pump capable of delivering a 10ml to 30ml dose at 1 ml/minute

### ***Appendix F.2        Reconstitution of Thrombosomes***

Patients will require at least one vial of Thrombosomes to be reconstituted. Aseptic technique must be used in the preparation of material. Thrombosomes should be infused within one hour of reconstitution

All reconstituted Thrombosomes vial(s) should be retained at 4°C on site for at least 7 days after infusion and be destroyed at the site as a biological material after completion of the study. Unused, unopened vial(s) of Thrombosomes will be returned to Cellphire.

**To rehydrate Thrombosomes:**

1. Remove vial(s) from room temperature storage and visually inspect for integrity. If there are signs of breakage, damage to the seal or atypical appearance of the contents, do not use and contact Cellphire. Record on the source document the vial(s) lot number, vial number, expiration date and other information as indicated on the form. Record product information about the WFI and other supplies on the source document.
2. Carefully remove any outer packaging from the vial(s). Remove the tab of the protective cap of the vial(s) stopper, exposing the grey butyl stopper, but leaving the collar of the aluminum seal in place. Swab with an alcohol wipe
3. Swab the port on the WFI bag with an alcohol wipe [if exposed] and place a medication injection site in the port of the bag if needed. Using this site and an appropriate sterile syringe, withdraw 10 ml WFI as indicated on the vial(s) label.
4. Using a CSTD puncture the exposed stopper to allow venting of air. Keep CSTD in place.
5. Attach the syringe containing the WFI to the luerlock of the CSTD and slowly deliver the WFI to the vial(s) through the rubber stopper. Gently tip the CSTD/syringe, directing the stream against the inside side wall of the vial(s), not onto the cake. Keep CSTD and syringe in place.
6. Record the start time/date of reconstitution on the vial(s) and on the source document.
7. Gently swirl the vial(s) every few minutes until 10 minutes or the entire cake is resuspended. Rehydrated Thrombosomes should appear off-white and translucent in suspension. Note: If the product does not reconstitute within 10 minutes or demonstrates excessive clumping or discoloration upon visual inspection, do not use for transfusion and contact Cellphire. In either case an alternate vial should be selected for rehydration.
8. Thrombosomes should be transfused within one hour of the end time of reconstitution.

**Appendix F.3        Preparation of Doses of Thrombosomes**

A dose table will be provided with each lot in the EDC. The method used to calculate dose is shown below.

For example: Patient weight = 70 kg  
Label indicates a dosage of 0.1 ml/kg body weight  
 $70 \times 0.1 = 7.0$  ml infusion dose.

In this example, the 7.0 ml infusion dose requires reconstitution of one 10 ml vial of Thrombosomes. If the volume calculated exceeds 10 ml, reconstitute additional number of vial(s) as required.

Once reconstitution of the Thrombosomes is complete:

9. While the CSTD/syringe in place, withdraw the volume of Thrombosomes based on the calculated dose for the patient being treated. Remove the syringe from the luerlock of CSTD.
10. Attach the sterile filter to the syringe and cover filter end with a sterile tip cap.
11. Attach syringe label with the designated recipient's ID number, product lot number, vial number and expiration (date/time) of reconstituted material and other pertinent identification information required by local procedures.
12. Provide to the responsible study personnel for infusion.
13. After infusion, place reconstituted vial(s) in 4°C storage.

## **Appendix G – Modified Definition of Anaphylaxis**

(Supplement from Symposium on the Definition and Management of Anaphylaxis: Summary report Sampson, Hugh A. et al. Journal of Allergy and Clinical Immunology, Volume 115, Issue 3, 584 – 591 and NHSN Hemovigilance Criteria.)

**Anaphylaxis is defined when any 1 of the 3 criteria are fulfilled:**

1. Acute onset of an illness (up to 4 hours post-infusion) with involvement of Skin/mucosal tissue (eg, hives, generalized itch/flush, swollen lips/tongue/uvula), and Airway compromise (eg, dyspnea, wheeze/bronchospasm, stridor, reduced PEF), or Reduced Blood Pressure\* or associated symptoms (eg, syncope)
2. Two or more of the following after exposure to known allergen for that patient (up to 4 hours post-infusion)  
History of severe allergic reaction  
Skin/mucosal tissue (eg, hives, generalized itch/flush, swollen lips/tongue/uvula)  
Airway compromise (eg, dyspnea, wheeze/bronchospasm, stridor, reduced PEF)  
Reduced BP\* or associated symptoms (eg, syncope)
3. Hypotension\* after exposure to known allergen for that patient (up to 4 hours post-infusion)  
\*Systolic BP <100 mm Hg or >30% drop from their baseline

BP: Blood pressure PEF: peak expiratory flow.

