### **1.9.2.1 All Cohorts**

Informed consent will be obtained from thrombocytopenic (platelet count  $\geq$  5,000/  $\mu$ L and  $\leq$  70,000 per  $\mu$ L) patients who are actively bleeding or are at risk of active bleeding within the 4 weeks of initial screening. Patients are eligible who have had a documented bleeding episode(s) within the previous 4 days of screening. If they pass screening, they will be enrolled and infused. Patients who are not actively bleeding, but who are at risk for active bleeding based on medical history and prognosis (projected clinical course) within 4 weeks from their initial screening, will be monitored for active bleeding. If the patient was not actively bleeding at the time of screening, but bleeding occurs within 4 days (+ 6 hours) of initial screening, the patient does not need to be rescreened, but must have a WHO bleeding assessment and a CBC at baseline. If the patient was not actively bleeding at the time of screening, but bleeding occurs greater than 4 days and within 4 weeks of initial screening, the patient will be rescreened, enrolled and infused. Patients who are not infused within 4 weeks of initial screening are withdrawn from study. Patients who were withdrawn from study may be re-entered into study if they were: 1) previously not infused with Thrombosomes, and 2) meet all the enrollment requirements of study. All enrolled patients will be assigned to cohorts based on order of enrollment and timing of infusion of Thrombosomes.

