not an exclusion to study participation. Subjects receiving antibiotics either to treat an infection or as expectant treatment of a clinically-suspected infection are excluded from study enrollment until the infection is resolved or ruled out. Subjects receiving prophylactic antibiotics to prevent an infection are not excluded from study.

13. Systolic blood pressure greater than 160 mmHg or lower than 90 mmHg; or diastolic pressure higher than 100 mmHg.
14. Treatment with any investigational agent within one month before treatment infusion for this trial, other than for treatment of their underlying disease.
15. Unwilling or unable to comply with the requirements of this protocol, including the presence of any condition (physical, mental, or social) that is likely to affect the patient's return for follow-up visits on schedule as determined by the investigator.
16. Other unspecified reasons that, in the opinion of the Investigator or Medical Monitor, make the patient unsuitable for enrollment.
17. Patient is institutionalized because of legal or regulatory order.

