Hemodynamic Instability			
 
• Any bleeding associated with moderate hemodynamic instability (hypotension; <math>>30</math>mmHg fall or <math>>30\%</math> decrease in either systolic or diastolic blood pressure) and requiring RBC transfusion over routine transfusion needs**
 

* Count actual bleeding (i.e. “running out” or need for basin, Kleenex, towel, etc.) not minor bleeding
 
** Red cell transfusion must be specifically related to treatment of bleeding within 24 hours of onset of bleeding
			

For inclusion, Grade 1 subset bleeding includes epistaxis, hematuria, oral petechiae, oropharyngeal bleeding, or bleeding at invasive or other wound sites. See bolded items above.
			

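### Appendix G: for a patient with no documented allergy to a product component, an airway reaction with a blood-pressure fall but no skin signs appears to fall outside the anaphylaxis stopping event

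*Protocol*

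**What the plan says.** Protocol section 1.9.8 names four stopping events: death, thrombotic or embolic event, acute lung injury and anaphylaxis. Each must be an SAE rated probably or definitely related. The window is 48 hours, or 4 hours for anaphylaxis. The section sends the reader to Appendix G for the definition of anaphylaxis, and SAP section 3.2 refers to the same appendix.

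Appendix G is satisfied by one of three criteria, each within 4 hours:

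- Criterion 1 joins skin or mucosal involvement by *and* to airway compromise, then by *or* to reduced blood pressure or related symptoms. There are no brackets.
- Criterion 2 is "Two or more of the following after exposure to known allergen for that patient (up to 4 hours post-infusion". Its four items are "History of severe allergic reaction", skin or mucosal signs, airway compromise, and reduced blood pressure.
- Criterion 3 is hypotension alone, under the same known-allergen condition.

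The footnote defines reduced pressure as "Systolic BP <100 mm Hg or >30% drop from their baseline".

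Protocol Table 2 gives one infusion in every cohort. Section 1.9.2.1 lets a withdrawn patient re-enter only if "previously not infused with Thrombosomes". Neither document says that Thrombosomes is to be treated as a known allergen.

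**The concern.** A condition that the allergen be already known for the patient suits someone re-exposed to a substance that has harmed them before. In this trial every infusion is the patient's first within the study. Two of the three criteria are therefore closed to most product reactions unless the patient has a documented allergy to something in the product. The documents do not show how common that is. The history footnote to Table 4 says "History to include previous transfusion with red blood cells, plasma and/or platelets" and does not mention reactions to those transfusions.

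If criterion 1 in turn requires skin signs, whether a related reaction with bronchospasm and a falling pressure counts as anaphylaxis depends on whether hives or flushing appear. Two consequences could follow. The event would be handled under the suspension rule instead of the stopping rule, and it might not be counted as anaphylaxis in the safety outputs.

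**Working it through.** The plan states no figure to reproduce. The check is a truth table on the Appendix G wording.

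**Inputs.** S = skin or mucosal signs, A = airway compromise, B = reduced blood pressure or related symptoms, all within 4 hours. The patient is at the first infusion with no known allergen, so criteria 2 and 3 are false. There are 2 × 2 × 2 − 1 = 7 non-empty presentations, of which 4 have two or more signs.

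**Two readings of criterion 1.** Reading 1 is S and (A or B). Reading 2 is (S and A) or B.

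| Presentation | Current, reading 1 | Current, reading 2 | Criterion 2 reworded, criterion 1 bracketed |
|---|---|---|---|
| S | no | no | no |
| A | no | no | no |
| B | no | yes | no |
| S + A | yes | yes | yes |
| S + B | yes | yes | yes |
| A + B | **no** | yes | **yes** |
| S + A + B | yes | yes | yes |
| Met | 3 of 7 | 5 of 7 | 4 of 7 |

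**Which reading is natural.** Under reading 2, a pressure fall alone meets criterion 1 with no allergen condition, so criterion 3 could never add a case. Reading 1 leaves criterion 3 a function for patients with a known allergen. Reading 1 is therefore the more likely intention, but this is an inference.

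**Result.** Under reading 1 the current text captures 3 of the 4 presentations with two or more signs and misses A + B. These are unweighted counts of presentations, not frequencies.

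**Checks on the fix.**

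- If criterion 2 is tied to the infusion but the history item stays, a patient with that history starts with one item counted. Any single sign then gives two, and 7 of 7 presentations qualify.
- If criterion 3 is also tied to the infusion, B alone qualifies and the count becomes 5 of 7.

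**What the classification changes.** The two routes in section 1.9.8 compare as follows:

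| | Suspension | Stop |
|---|---|---|
| Relatedness needed | possible, probable or definite | probable or definite |
| Who reviews | DMC, with the Medical Monitor and the treating PI | medical monitor, all PIs and the DMC, over the full data |
| Condition for going on | DMC recommendation; no set standard | finding of reasonable doubt that the event is related |

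After a suspension the DMC can recommend proceeding even if it judges the event related. After a stop, the reasonable-doubt condition rules that out.

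**The case against.** The strongest reply is that patients are already protected, and this largely stands. A related SAE that is not a stopping event halts both enrollment and infusion, with an ad hoc DMC review that may recommend not proceeding. Under section 1.9.2.1 no one else is infused until the last patient reaches Day 4 without a suspension or stopping event. A fatal reaction rated probably or definitely related within 48 hours would stop the trial as a death. A reader might infer that a severe reaction could pass without a halt; the documents do not support that.

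Second, the gap depends on an inferred grouping. Under reading 2 the event is captured, and page layout lost in the text extraction may have shown the intended structure. This stands as a qualification.

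Third, a reader might infer that the event would certainly be absent from the anaphylaxis outputs. SAP 8.1 and the listing of thromboembolic, stroke, lung-injury and anaphylaxis events do not say who classifies events or that Appendix G governs them. Protocol 1.22.6.1 asks investigators to establish a diagnosis, 1.22.6.3 brings in hemovigilance criteria, and events are coded in MedDRA. Omission is possible, not certain, and the event stays in the general TEAE and SAE tables in any case.

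Fourth, Table 5 might be read as showing that airway reactions without skin signs are expected, because breathing difficulty has its own line. But the allergic-reaction line, which begins with flushing, itching and hives, itself ends with "difficulty breathing, chest pain, or bronchospasm, which may vary in severity from mild to life-threatening". The next line looks like a repeated fragment of it, and neither line mentions blood pressure.

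Finally, section 1.9.7 leaves stopping rules partly to a DMC charter that is not among the documents and might settle the matter.

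**Conclusion.** The point holds as a minor wording defect in an operative safety definition. It rests on three conditions: criterion 1 is read as skin and (airway or reduced pressure), the patient has no documented allergy to a product component, and nothing outside the two documents treats Thrombosomes as a known allergen. Under these conditions one of the four presentations with two or more signs falls outside the stopping event. The loss is the stricter restart condition, plus possible omission from the anaphylaxis summary and listing. The documents give no rate for such reactions, so no probability of an affected decision is offered.

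A reader might also infer that the blood-pressure footnote is wrong, because exclusion criterion 13 bars only "Systolic blood pressure greater than 160 mmHg or lower than 90 mmHg" (and high diastolic pressure). A patient can therefore enter at 90 to 99 mmHg and already be under the footnote's limit. That is not a reason to change it. An over-inclusive pressure threshold is a defensible choice in a Phase 1 safety trial, and a stop still needs an SAE rated probably or definitely related.

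**What to change.** Amend Appendix G as follows:

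1. In criterion 2, replace the known-allergen condition with the Thrombosomes infusion, and remove allergic history from the countable items. Two or more of skin or mucosal signs, airway compromise and reduced blood pressure within 4 hours then qualify.
2. Bracket criterion 1 as skin and (airway or reduced pressure), if the original layout does not already show this. Without it, reading 2 would still let a pressure fall alone count.
3. Leave criterion 3 as it is, so that isolated hypotension after the infusion is not labelled anaphylaxis.
4. Leave the blood-pressure footnote as it is.

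By its logic the new criterion 2 also covers the bracketed criterion 1; keeping both does no harm.

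The cost is appendix wording in a protocol amendment, submitted to the IRB and FDA under section 1.22.4. The SAP refers to the appendix and needs no separate definition. No new data are required: Table 4 already schedules a pre-infusion reading and 120/15 = 8 quarter-hourly readings to 2 hours, then readings at 3 and 4 hours, so 10 after the start of infusion.

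The downside is that slightly more events may meet the definition, including an airway sign in a patient whose systolic pressure was already 90 to 99 mmHg. The relatedness and seriousness requirements of the stopping rule limit this.
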